## Section 2 - Study Population Characteristics (Study 1)

### 2.1. Conditions or Focus of Study

- Secondary Prevention
- Driving Under the Influence
- Accident Prevention
- Alcoholic Intoxication
- Alcohol Drinking

### 2.2. Eligibility Criteria

The project has two relevant, linked target populations: 1) concerned family members (CFM) of driving while intoxicated (DWI) offenders and 2) the first-time DWI offenders themselves. The inclusion/exclusion criteria for these populations are as follows.

#### DWI Offender:

- male or female
- 21 years or older
- first-time DWI offender with IID installed in vehicle
- enrolled in Santa Fe County DWI Program
- have a smartphone, tablet computer, or personal computer with Internet access
- consent to participate
- able to read and speak English or Spanish

#### Concerned Family Member (CFM):

- male or female
- 21 years or older
- spouse, parent, or immediate family member of first-time DWI offender with IID installed in vehicle and enrolled in Santa Fe County DWI Program
- have a smartphone, tablet computer, or personal computer with Internet access
- consent to participate
- able to read and speak English or Spanish

#### Exclusion Criteria:

- other family members already enrolled in the project
- second or above DWI conviction

2.3. Age Limits	Min Age: 21 Years	Max Age: 85 Years
2.4. Inclusion of Women, Minorities, and Children	2.4_BSMART.pdf	
2.5. Recruitment and Retention Plan	2.5_BSMART.pdf	
2.6. Recruitment Status	Not yet recruiting	
2.7. Study Timeline	2.7_BSMART.pdf	
2.8. Enrollment of First Subject	06/01/2019	Anticipated

## **2.4. INCLUSION OF WOMEN, MINORITIES, AND CHILDREN**

### **Inclusion of Women and Minorities**

Potential participants will not be excluded based on ethnic group or race. We will attempt to recruit participants at similar rates to the 2014 New Mexico DWI Offender Characteristics and Recidivism Report. According to the Report, the race/ethnicity of the DWI offender population in New Mexico from 2003 through 2013 were as follows: 49% Hispanic, 28% White, 20% American Indian/Alaska Natives, and 3% African American. The gender of the DWI offender population was 72% male and 28% female. The Targeted Enrollment Table represents a composite of these numbers.

During the recruitment process, the UNM project coordinator will screen for participants using IRB-approved protocols for screening based on gender, race, and ethnicity. If the project coordinator finds that we are over-recruiting a particular gender or racial or ethnic group, we will place them on a waiting list until we have recruited an adequate number of targeted participants

### **Inclusion of Children**

[figure not shown]
Children under 18 will be ineligible for participation. Children under 18 will not be enrolled in the proposed project because this app is aimed at adults. We are limiting age to no younger than 21 years old because DWI offenders under age 21 fall under a different set of laws and court programs than offender 21 or older. To keep things simple, we will also limit the age of CFMs to 21 years or older. Age will be self-reported by the participants.

Human Subjects oversight will be conducted by the Western Institutional Review Board (WIRB; DHHS IRB Reg. No. 00000533). The IRBs will approve all consenting procedures (including recruitment advertisements, posters, recruitment letters and consent forms), intervention protocols, survey instruments and data collection protocols, and data management procedures prior to study implementation and prior to the recruitment of any participants.

The investigative team has extensive experience from previous community-based trials and as a result already have a rich inventory of recruiting materials and protocols to be used for this study, including materials and protocol used to recruit DWI offenders and CFMs to the Phase I research. We will recruit 300 eligible DWI offenders and 300 eligible CFMs to complete the baseline assessment and be randomized. That way, at least 255 DWI offenders and 255 CFMs will complete the 9-month follow-up (85% retention).

Potential participants will be contacted for recruitment and consenting at monthly Santa Fe County DWI program meetings held for each DWI offender at the beginning of her/his probation period. CFMs of first-time DWI offenders will be contacted via email and a web recruitment portal designed exclusively for the project and followed up with a recruitment phone call. Participants will only be enrolled in the trial if both the DWI offender and CFM consent to participate. Our previous work in Phase I of the project found a strong willingness to participate in the project among both DWI offenders and CFM based on their interest in better family functioning and the unique convenience of a *B-SMART mobile web app* that could be beneficial to their experiences with the IID. In New Mexico, Santa Fe County had the fourth-highest ranked number of first time DWI offenders (360) in 2015 and 313 first time convictions in 2016.

The Project Coordinator will track participants and report on progress in recruiting women and ethnic/racial minorities. The study data team will provide detailed reports describing overall recruitment, as well as with strategies for recruiting women and ethnic/racial minorities. To retain participants, participants will fill out a locator form with contact information (name, address, telephone numbers [landline and cell], and email address) and collateral contact information (i.e., a person close to them who can reach them if they do not respond to follow-up communication from the study) to locate them for assessment at the 3-month and 9-month follow-ups. Prior to the posttests, study staff will text and email the participants to remind them of the upcoming posttest survey. Once invitations are issued for the follow-up surveys, reminders to complete the follow-up survey will be sent by email and text at 5-day intervals for two weeks. To reach persistent non-responders, staff will send printed/PDF copies of posttests by mail (with a stamped return envelope) and email. Although participants can withdraw at any time, steps will be used to minimize dropouts to ensure high internal validity. Participant progression will be tracked. Staff will use behavioral reinforcement strategies known to be effective in the behavior change literature and be trained to develop rapport with participants by communicating expectations for participants and staff. We will compare dropouts to those retained to determine if there is any potential bias. We have employed these retention procedures in prior trials, keeping average loss across 9 months at 15%-20%.

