### 3C.6. Randomized Trial Evaluating *B-SMART* (Specific Aim 4; Months 8-24)

**3C.6.1. Experimental Design.** The *B-SMART mobile web app* will be evaluated in a randomized pretest-posttest controlled design. In months 6-11, first time DWI offenders and CFMs will be recruited for participation in the trial. First-time DWI offenders and their CFMs will be randomized together to the intervention (*B-SMART*)

(n=150) or a usual and customary (UC) IID information condition comparison group (n=150) following baseline assessment. Assessment via web-based surveys will be conducted with the DWI offenders and CFMs at baseline, 3-month follow-up, and 9-month follow-up

post randomization. Also, information on frequency of alcohol-positive IID tests (termed “lockout events”) will be acquired by the project from the Santa Fe County and Municipal DWI Program at the 9-month assessment point (posttest only) for each DWI offender. Thus, the proposed efficacy trial (see **Figure 5**) will be a 2 (level of treatment – app intervention vs. UC information) x 3 (level of time – baseline vs. 3-month follow-up vs. 9-month follow-up) mixed factorial design. Baseline and follow-up data collection will be conducted via online surveys and a customized web portal and include DWI offender and CFM alcohol frequency and use measures and measures of family communication and functioning (see 3C.7). Participants will fill out a locator form with contact information and collateral contact information to locate them for assessment at the 3-month and 9-month follow-ups. We have employed these locator procedures in prior trials, keeping average loss across 9 months at 15%-20%. Cumulative IID lockout event data will be collected for all DWI offenders from the Santa Fe County DWI Program at the 9-month assessment point.

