**3C.6.5. Sample Size Determination.** The sample size for the randomized trial in the Phase II research is designed to provide sufficient information for Phase III commercialization. The sample size assumes the counts of interlocks are Poisson distributed. We have assumed 4 interlocks over 9 months in the control arm or a rate of 0.44 per month for each DWI offender. In the *B-SMART mobile web app* group, we have assumed a reduction of 40% from 0.44, resulting in a rate of 0.27 per month. The null hypothesis is that the ratio of these two rates is 1.0 versus 0.6. Assuming a Type I error of 0.05 (2-sided), 90% power, sample size is only 27 DWI offenders per group. However, if the rate is higher up to 1 per month, the sample size required declines since the percent reductions yield wider absolute differences in the rates. We also are keen to know the reductions achievable with the *B-SMART* group, so we evaluated the sample size with regards to other effect sizes. A Cochrane meta-analysis reported the impact of IIDs to reduce risk by 64%, but with a confidence interval that ranged from 76% to 37%. In the proposed trial, we have two treatment groups and may see less impact than that in the meta-analysis. Thus, a sample size of 119 DWI offenders per group will allow for 90% power with a comparison of 0.44 to 0.36 or approximately a 20% reduction in interlocks. We will adjust for an expected 15% attrition and this sample size also has sufficient sample size to evaluate the impact in various gender and ethnic subgroups. Thus, we propose to randomize 150 DWI offenders and 150 CFMs to each arm of the trial.

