## 3C.7. Outcome Measures

**3C.7.1. Measure of Primary Outcome Variable: IID Lockout Events.** The primary outcome

measure will be frequency of IID lockout events from baseline to 9-month follow-up post-randomization, collected from the Santa Fe DWI program database for each first-time DWI offender participant. Marques, Voas and colleagues have demonstrated in a series of investigations that frequency of lockout events strongly predicts DWI recidivism over time, and as such, IID lockout events are an important and useful proxy measure for DWI recidivism. Given the length of time necessary to accumulate DWI recidivism data (average length of time varies across locales and can be between 2 and 8 years), IID lockout events provide a direct and accessible measure of DWI recidivism within the two-year project timeline.

**3C.7.2. Measures of Secondary Outcome Variables and Mediators.** Alcohol use by the DWI offender, a secondary outcome, will be assessed at baseline, 3-month follow-up, and 9-month follow-up with versions of the Form 90 adapted for online assessment for the CFMs (Form 90-ACS) and first-time DWI offenders (Form 90-AF). The Form 90 measures produce detailed quantity and frequency measure of alcohol use for the first-time offender that are validated by the CFM reports. Family functioning will be assessed at baseline, 3-month follow-up, and 9-month follow-up, as potential mediators of *B-SMART* effects, with DWI offenders and CFMs with three measures: (1) Family Environment Scale – Cohesion and Conflict subscales assesses offender and CFM perceptions of positive and negative family functioning; the two subscales selected are strongly associated with treatment outcome; (2) Family Communication Scale from FACES-IV assesses perception of quality of communication in the family; (3) Pleasant Events Schedule (adapted) assesses shared positive activities within a family. These three measures are also being used in the B-FIT study, allowing for comparison of outcomes across the two studies.

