**Planned Analysis for Hypothesis 1.** The second major analysis will focus on impact of the *B-SMART mobile web app* on primary (IID lockout events) and secondary (DWI offender's alcohol consumption) outcomes and be completed within 1 month of the end of the posttest data collection in Year 2. The effect of *B-SMART* on IID lockout events in Hypothesis 1 will be tested primarily using PROC GENMOD with a Poisson link via SAS Version 9.4, which includes capabilities to test these Poisson models with missing data, account for the temporal design, and include information by participant. Participants will be treated as a random effect and treatment as a fixed effect, at  $p=0.05$  (2-sided). Analyses of primary outcomes will not be released before completion of the intervention. Since CFM and DWI offender can be clustered within the same family, hierarchical models with participants nested within families will be considered.

The secondary outcome of quantity and frequency of alcohol consumption by DWI offenders will be compared in several ways. Quantity and frequency will be evaluated using Poisson models, as well as a composite variable based on total alcohol consumption (the product of the two variables), using negative binomial regression models, unless a Poisson model is sufficient.

Since date of IID lockout events will be collected and alcohol consumption is measured at all three assessments, we will examine the time by treatment interaction in the analyses of Hypothesis 1 to assess the

question of the durability of the effects of B-SMART over time. For example, we will evaluate time to first lockout using a Kaplan Meier approach and the times to subsequent lockouts.

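### The only stated attrition check does not call for a comparison by arm, and the SAP names no missing-data method for the survey outcomes

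*Combined protocol and SAP*

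**What the plan says.** The recruitment and retention text (Section 2, printed after Inclusion of Children) gives the whole attrition-bias plan: "We will compare dropouts to those retained to determine if there is any potential bias". It names no arm, variable, time point or role (offender or concerned family member, CFM), and no action if a difference is found.

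The SAP (Planned Analysis for Hypothesis 1; same text in protocol 3C.8.2) adds no attrition analysis. It says that the Poisson models will be run in PROC GENMOD, "which includes capabilities to test these Poisson models with missing data". No method, missingness assumption or sensitivity analysis is named.

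On the amount of loss, the sample size section says "We will adjust for an expected 15% attrition". Section 3C.6.1 and the retention text report 15% to 20% loss over nine months in earlier trials, and the retention target is 255 of 300 in each role.

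Two other sources bear on offenders who stop answering surveys:

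- Section 3C.6.1: "Cumulative IID lockout event data will be collected for all DWI offenders", taken from program records at the 9-month point.
- Section 3C.7.2: "The Form 90 measures produce detailed quantity and frequency measure of alcohol use for the first-time offender that are validated by the CFM reports". CFMs are surveyed at baseline, 3 and 9 months.

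Section 3.2.A limits both: once a participant withdraws, nothing further is collected, although earlier data are kept.

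**The concern.** Attrition biases a treatment comparison when the people lost differ between the arms. A contrast of all dropouts with all completers does not measure that. If heavier drinkers leave one arm and lighter drinkers leave the other, the overall contrast can be null while the retained groups are no longer comparable. Different dropout by arm is plausible, because the app may take up to 120 minutes (3C.6.3) and the control arm receives a pamphlet.

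A software capability is not a missing-data method. GENMOD omits records with a missing response, and ordinary GEE estimates hold only if loss is unrelated to drinking, given the covariates in the model. The Form 90 secondary outcome and the H2 mediators come from surveys. An apparent effect on them could reflect who stayed, while the stated check reports nothing unusual.

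**Working it through.** **1. Number lost.** 300 × 0.85 = 255, which reproduces the plan's retention figure. Loss is 300 × 0.15 = 45 to 300 × 0.20 = 60 offenders. The documents give no split by arm, or between non-response and withdrawal.

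**2. Unequal rates.** With 150 per arm ("randomize 150 DWI offenders and 150 CFMs to each arm of the trial"), 10% against 20% dropout is 15 against 30 people. That is the same total of 45 as 15% in each arm. A two-sided 5% comparison of dropout by arm has power of 31% for 12% v 18%, 68% for 10% v 20%, and 96% for 7.5% v 22.5%. A tabulation that ignores arm shows 45 in every case.

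**3. Opposite patterns.** Assume 15% dropout per arm, with dropouts +0.5 SD from completers on a baseline variable in one arm and -0.5 SD in the other.

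- Contrast ignoring arm: (0.5 - 0.5)/2 = 0.
- An arm's retained mean moves by -0.15 × D, where D is the dropout-minus-completer difference. The retained arms therefore differ by 0.15 × (0.5 + 0.5) = 0.15 SD.
- Arm-by-dropout interaction: the within-arm SE is √(1/22.5 + 1/127.5) = 0.229, so the interaction SE is 0.229 × √2 = 0.323. Then 1.0/0.323 = 3.09, and power is Φ(3.09 - 1.96) = 87%.

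**4. Effect on a completers-only test.** Assume no true effect, 150 per arm, log drinking at follow-up with SD 1, and dropout that depends on being above or below the median at follow-up. The mean of either half is ±√(2/π) = ±0.798.

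*Worst case, mirror image:* heavier and lighter drinkers drop out at 30% and 5% in the app arm, reversed in control (17.5% loss per arm).

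- Retained app mean: 0.798 × (0.70 - 0.95)/(0.70 + 0.95) = -0.121. Control is +0.121.
- Bias: -0.24, a ratio of exp(-0.24) = 0.79.
- Retained per arm: 150 × 0.825 = 123.75. SE ≈ √(2 × (1 - 0.121²)/123.75) = 0.126.
- Rejection at 5%: Φ(0.242/0.126 - 1.96) ≈ 48%.

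*Milder case:* 25% and 15%, reversed between arms (20% loss).

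- Bias: 2 × 0.798 × (0.75 - 0.85)/1.60 = -0.10. SE ≈ √(2/120) = 0.129.
- Rejection: about 12%.

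Simulation agrees: 45% to 53% and 11% to 14%.

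**5. What the remedies achieve.** The simulation adds these assumptions: correlation 0.5 between baseline and follow-up drinking, 0.7 between the CFM report and offender drinking, and 0.3 to 0.5 between drinking and lockouts. None of these is in the documents.

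| | Worst case | Milder case |
|---|---|---|
| Completers-only rejection | 45%-53% | 11%-14% |
| After imputation | 15%-35% | 6%-11% |

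In the worst case, a baseline check that ignores arm flags about 5%, which is chance. The by-arm lockout check flags about 26% to 66%, rising with the drinking-lockout correlation. In the milder case the by-arm checks have low power. Worst-case rejection after imputation is 15%-18% with CFM reports for every dropout, 24%-29% with 43% coverage and 28%-35% with none. Completers adjusted for baseline reject 37%-42%.

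**6. CFM coverage.** With dropout d in each role and within-pair dropout correlation ρ, the share of offender dropouts whose CFM still responds is (1 - d)(1 - ρ). At d = 0.15 this is 85% for ρ = 0, 64% for 0.25, 43% for 0.5 and 0% for 1. It falls below half when ρ exceeds (0.5 - d)/(1 - d): 0.35/0.85 = 0.41 at 15% loss, and 0.30/0.80 = 0.375 at 20%.

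**The case against.** The retention sentence does not say that the arms are pooled. A reader might infer that the check cannot detect arm-specific dropout, but the text is silent and an analyst could stratify. This stands. The defect is that nothing commits the analyst to the informative comparison.

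A reader might also infer that lockout counts and CFM reports exist for most survey dropouts. The documents do not support that. Section 3.2.A ends collection at withdrawal, and step 6 shows that CFM coverage depends on a correlation that is not given. Sections 3C.2 and 3.1.A define the CFM as living with the offender, which makes linked dropout plausible.

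The mirror-image pattern is chosen so that the overall contrast cancels, and nothing in the documents predicts it. It is a worst case. The milder case gives modest inflation, and there the by-arm checks would often miss the problem.

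The SAP also calls participants a random effect over repeated assessments. A likelihood model of that kind would use the baseline and month-3 data of people lost later, so completers-only is not certain to be the planned analysis. But the SAP names GENMOD, and baseline adjustment alone leaves rejection at 37% to 42% in the worst case.

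Finally, the Analysis Subcommittee is to write a detailed analysis plan. That does not repair the present SAP.

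**Conclusion.** The concern holds for the secondary drinking outcome and the H2 mediators. The one attrition check does not specify comparison by arm, and no missing-data method is stated for an expected 45 to 60 offenders lost. The possible distortion runs from 11%-14% false rejection in the milder pattern to 45%-53% in the worst case. All these figures rest on assumed dropout patterns and correlations. Imputation reduces the bias and does not remove it, because dropout in these scenarios depends on drinking that was not observed.

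It would be wrong to infer that survey dropout undermines the primary analysis. Lockout counts come from program records, so a missed survey does not lose them. Withdrawal can: the counts are acquired at month 9, and Section 3.2.A stops collection at withdrawal, which conflicts with collecting them for all offenders. The share who will withdraw is not given. The point merits a change to the SAP but does not threaten the trial's main conclusion.

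**What to change.** Replace the retention sentence and add to the SAP:

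1. Report dropout and withdrawal by arm and by role. Test arm-by-dropout interaction on baseline Form 90 drinking and on the lockout count. State that a null result is weak reassurance, given the low power in milder patterns.
2. Analyse Form 90 drinking and the mediators by multiple imputation, or an equivalent likelihood model, that includes arm, baseline value, month-3 value, lockout count and the CFM's Form 90-ACS report where present. Keep the completers analysis as a sensitivity analysis.
3. Reconcile Section 3.2.A with 3C.6.1: say whether lockout counts of withdrawn offenders are obtained, and for what period.

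No extra CFM survey is needed, because CFMs are already surveyed at every wave. The cost is wording and some additional analysis, with no new data, staff or participants. The imputed estimate may look slightly less precise than the completers estimate.

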**FIGURE 2: Study Timeline**

**Inclusion Enrollment Reports**

Entry#	Enrollment Location Type	Enrollment Location
Study 1, IER 1	Domestic	New Mexico

**Inclusion Enrollment Report 1**Using an Existing Dataset or Resource\* :  Yes  NoEnrollment Location Type\* :  Domestic  Foreign

Enrollment Country(ies): USA: UNITED STATES

Enrollment Location(s): New Mexico

Comments: 32/Focus Group; 32/Usability testing; 600/Randomized Control Trial

**Planned**

Racial Categories	Ethnic Categories				Total	
	Not Hispanic or Latino		Hispanic or Latino			
	Female	Male	Female	Male		
American Indian/ Alaska Native	37	96	0	0	133	
Asian	0	0	0	0	0	
Native Hawaiian or Other Pacific Islander	0	0	0	0	0	
Black or African American	6	14	0	0	20	
White	52	134	91	234	511	
More than One Race	0	0	0	0	0	
Total	95	244	91	234	664	

**Cumulative (Actual)**

Racial Categories	Ethnic Categories								Total	
	Not Hispanic or Latino			Hispanic or Latino			Unknown/Not Reported Ethnicity			
	Female	Male	Unknown/ Not Reported	Female	Male	Unknown/ Not Reported	Female	Male		
American Indian/ Alaska Native	0	0	0	0	0	0	0	0	0	
Asian	0	0	0	0	0	0	0	0	0	
Native Hawaiian or Other Pacific Islander	0	0	0	0	0	0	0	0	0	
Black or African American	0	0	0	0	0	0	0	0	0	
White	0	0	0	0	0	0	0	0	0	
More than One Race	0	0	0	0	0	0	0	0	0	
Unknown or Not Reported	0	0	0	0	0	0	0	0	0	
Total	0	0	0	0	0	0	0	0	0	

